4.1.2. Definition

4.1.2.1. Baseline definition

For all endpoints the baseline value will be the latest pre-dose assessment with a non-missing value, including those from unscheduled visits. If time is not collected, Day 1 assessments are assumed to be taken prior to first dose and used as baseline.

Unless otherwise stated, if baseline data is missing no derivation will be performed and baseline will be set to missing.

4.1.2.2. Worsening of pre-existing medical conditions and/or obstetric complications

Worsening of the pre-existing medical condition and/or obstetric complication will be considered by the investigator, using clinical judgment and the following criteria:

- Change in medication and/or medication dose
- Medically attended event in relation to pre-existing condition and/or obstetric complication that are outside the routine management of the condition/complication
- SAE and/or hospitalization in relation to pre-existing condition and/or obstetric complication

Worsening of the pre-existing medical condition and/or obstetric complication will be collected from Day 1 (Visit 1) up to Day 181 post-delivery as AESI.

4.1.2.3. RSV infection

The sponsor will analyse nasal swabs by quantitative reverse transcription polymerase chain reaction (qRT-PCR) for the presence of RSV-A/B. A positive (RSV-A or B) test result constitutes a case of RSV infection. Refer to Table 10, Table 12 and section 8.4 of the Protocol.

In the event the collection of a nasal swab for testing by the sponsor is impossible, results from locally collected samples, tested with locally approved tests, may also be considered for the determination of a case of RSV infection.

Note: Due to the change in the study requirements, RTI surveillance of the maternal participants will no longer be performed.

4.1.2.4. RTI and LRTI

RTI cases will be classified (during data analyses) according to the definitions provided in [Table 9*](#) and [Table 10](#).

**** Due to the change in the study requirements, RTI surveillance of the maternal participants will no longer be performed.***

Table 9 MA-RTI case definitions for data analysis in maternal participants

RSV-MA-RTI	Medically attended visit for RTI symptoms AND Confirmed RSV infection ^{1,2}
RSV hospitalization	Confirmed RSV infection AND Hospitalized for acute medical condition ³
All-cause MA- RTI	Medically attended visit for RTI symptoms

¹ Confirmed RSV infection defined in Section 4.2.5.3 of the Protocol

² RSV (nasal swab) sampling and testing as specified in Table 10 of the Protocol.

³ Hospitalization is defined as admission for observation or treatment based on the judgment of a health care provider.

MA-RTI = Maternal, medically attended respiratory tract illness

Note: Due to the change in the study requirements, RTI surveillance of the maternal participants will no longer be performed.

Table 10 RTI/LRTI case definitions for data analysis in infants

RSV-RTI	Runny nose, OR Blocked nose, OR Cough AND Confirmed RSV infection ⁴
RSV-LRTI	History of cough OR difficulty in breathing ¹ AND SpO ₂ < 95% ² , OR RR increase ³ AND Confirmed RSV infection ⁴
RSV-severe LRTI	Meeting the case definition of RSV-LRTI AND SpO ₂ < 93% ² , OR lower chest wall in-drawing, OR inability to feed, OR failure to respond / unconscious
RSV hospitalization	Confirmed RSV infection ⁵ AND Hospitalized for acute medical condition ⁶
All-cause RTI	Runny nose, OR Blocked nose, OR Cough
All-cause LRTI	History of cough OR difficulty in breathing ¹ AND SpO ₂ < 95% ² , OR RR increase ³
All-cause LRTI hospitalization	Hospitalized due to all-cause LRTI as defined above

Definitions are modified from [Modjarrad, 2016]; **RTI** = respiratory tract illness; **LRTI** = lower respiratory tract illness; **RR** = respiratory rate; **SpO₂** = blood oxygen saturation by pulse oximetry.

¹ Based on history reported by parents/LARs and includes difficulty in breathing (e.g. showing signs of wheezing or stridor, tachypnoea, flaring [of nostrils], chest in-drawing, apnea).

² For blood oxygen saturation (SpO₂), the lowest value monitored will be used. In high altitudes (>2500m), SpO₂ <92% for LRTI, <90% for severe LRTI.

³ RR increase defined as:

- > 60/minute (< 2 months of age)
- > 50/minute (2 to < 12 months of age)
- > 40/minute (12 to 24 months of age)

⁴ Confirmed RSV infection defined in Section 4.2.5.3 of the Protocol.

⁵ RSV (nasal swab) sampling and testing as specified in Table 12 of the Protocol.

⁶ Hospitalization is defined as admission for observation or treatment based on the judgment of a health care provider.

For the analysis of RTI episode, a new RTI episode will be defined as any occurrence of cough, runny nose, blocked nose, wheezing or difficulty breathing with an interval of at least 7 symptom free days since the last episode of RTI that was diagnosed.

4.2. Primary Endpoint(s) Analyses

4.2.1. Safety

4.2.1.1. Analysis of safety and reactivity planned in the protocol

Safety analyses in maternal participants will include summaries by study group and age category (<18 years; ≥ 18 years; overall) of solicited administration site and systemic events, unsolicited AEs, MAEs, SAEs, MA-RTIs, RSV-associated MA-RTIs, (S)AEs leading to study withdrawal, worsening of pre-existing medical conditions and/or obstetric complications, pregnancy outcomes and pregnancy-related AESIs.

Safety analyses in infant participants will include summaries by study group and gestational age at birth (≥ 37 weeks; <37 weeks; overall) of neonatal AESIs, MAEs, SAEs, (S)AEs leading to study withdrawal, and occurrence of RSV- associated LRTIs, severe LRTIs, RSV-associated hospitalization.

The reactivity analysis will be performed on Solicited Safety Set for maternal participants, and other safety analyses will be performed on the Exposed Sets for both maternal and infant participants.

	Primary Safety Endpoints	Statistical Analysis Methods
Maternal participants	Number and percentage of maternal participants reporting solicited administration site and systemic events during a 7-day (i.e. Day 1 to Day 7 included) follow-up period after dosing.	
The number and percentage with exact 95% CI of maternal participants reporting each solicited administration site event (any grade, each grade,) and solicited systemic event (any, each grade) during the 7-day (7 days post-study intervention, Day 1 included) follow-up period after dosing will be tabulated by maximum intensity per participant for each study group.
 
The number and percentage of maternal participants reporting:
 
 • at least one administration site AE (solicited and unsolicited) • at least one systemic AE (solicited and unsolicited) • any AE 
during the 7-day (7 days post-study intervention, Day 1 included) follow-up period after dosing will be tabulated with exact 95% CI by group.
 
The same computations will be done for Grade 3 solicited and unsolicited AEs, for any unsolicited AEs considered related to study intervention, for any Grade 3 unsolicited AEs considered related to study intervention and for any solicited and unsolicited AEs resulting in a medically attended visit (i.e., MAEs).

	Number and percentage of maternal participants reporting unsolicited AEs that occur during a 30-day (i.e. Day 1 to Day 30 included) follow-up period after dosing.	
The number and percentage of maternal participants reporting unsolicited AEs within 30 days (30 days post-study intervention, Day 1 included) after dosing with exact 95% CIs will be tabulated by group and by MedDRA preferred term.
 
Similar tabulations will be done for Grade 3 unsolicited AEs, for any causally related unsolicited AEs, for Grade 3 related unsolicited AEs and for MAEs.

CONFIDENTIAL

	Primary Safety Endpoints	Statistical Analysis Methods
	
Number and percentage of maternal participants reporting SAEs, (S)AEs leading to study withdrawal, and MAEs from Day 1 up to 42 days post-delivery.
	
The number and percentage of maternal participants reporting:
 
 • at least one SAE • at least one (S)AE leading to study withdrawal • at least one MAE 
from Day 1 up to 42 days post-delivery with exact 95% CIs will be tabulated by group and by Medical MedDRA preferred term.
 
By participant listings of SAEs, (S)AEs leading to study withdrawal, and MAEs will be prepared.

	
Number and percentage of maternal participants reporting pregnancy outcomes * from Day 1 up to 42 days post-delivery. *These include live birth with no congenital anomalies, live birth with minor congenital anomalies only; live birth with at least one major congenital anomaly, fetal death/still birth (antepartum or intrapartum) with no congenital anomalies, fetal death/still birth (antepartum or intrapartum) with only minor congenital anomalies, fetal death/still birth (antepartum or intrapartum) with at least 1 major congenital anomaly; elective/therapeutic termination with no congenital anomalies; elective/therapeutic termination with only minor congenital anomalies, and elective/therapeutic termination with at least 1 major congenital anomaly.
	
The number and percentage of maternal participants reporting each pregnancy outcome from Day 1 up to 42 days post-delivery will be tabulated with its exact 95% CI by group.
 
By participant listings of adverse pregnancy outcomes will be prepared.

	
Number and percentage of maternal participants reporting pregnancy-related AESIs * and worsening of pre-existing medical conditions and/or obstetric complications from Day 1 up to 42 days post-delivery. * These include maternal death, hypertensive disorders of pregnancy (gestational hypertension, pre-eclampsia, pre-eclampsia with severe features including eclampsia), fetal growth restriction, gestational diabetes mellitus, pathways to preterm birth (premature preterm rupture of membranes, preterm labor, provider-initiated preterm birth) and chorioamnionitis.
	
The number and percentage of maternal participants reporting each pregnancy-related AESI and worsening of pre-existing medical conditions and/or obstetric complications from Day 1 up to 42 days post-delivery will be tabulated with its exact 95% CI by group.
 
By participant listings of pregnancy-related AESIs and worsening of pre-existing medical conditions and/or obstetric complications will be prepared.

CONFIDENTIAL

	Primary Safety Endpoints	Statistical Analysis Methods
Infant participants	
Number and percentage of infant participants reporting neonatal / infant AESIs * from birth up to 42 days post-birth.
 
* These include small for gestational age, low birth weight including very low and extremely low birth weight (<2500 g, <1500g, <1000g), congenital anomalies (major external structural defects, internal structural defects, functional defects), neonatal death (in an extremely preterm birth [22<GA<28 weeks], in a preterm live birth [28<GA<37 weeks], or in a term live birth) and preterm birth.
	
The number and percentage of infant participants reporting each neonatal / infant AESI from birth up to 42 days post-birth will be tabulated with its exact 95% CI by group.
 
By participant listings of neonatal / infant AESIs will be prepared.

	
Number and percentage of infant participants reporting SAE, (S)AEs leading to study withdrawal, and MAEs from birth up to 42 days post-birth.
	
The number and percentage of infant participants reporting:
 
 • at least one SAE • at least one (S)AE leading to study withdrawal • at least one MAE 
from Day 1 up to 42 days post-birth with exact 95% CIs will be tabulated by group and by MedDRA preferred term.
 
By participant listings of SAEs, (S)AEs leading to study withdrawal and MAEs will be prepared.

	
Number and percentage of infant participants reporting SAEs, (S)AEs leading to study withdrawal, and MAEs from birth up to 180 days post-birth.
	
The number and percentage of infant participants reporting at least one SAE, (S)AE leading to study withdrawal, and MAE from birth up to 180 days post-birth will be tabulated with 95% CI by group.
 
By participant listings of SAEs, (S)AEs leading to study withdrawal and MAEs will be prepared.

	
Number and percentage of infant participants reporting SAEs, (S)AEs leading to study withdrawal, and MAEs from birth up to 365 days post-birth.
	
The number and percentage of infant participants reporting at least one SAE, (S)AE leading to study withdrawal, and MAE from birth up to 365 days post-birth will be tabulated with 95% CI by group.
 
By participant listings of SAEs, (S)AEs leading to study withdrawal and MAEs will be prepared.

AE= Adverse event; **CI**= Confidence interval; **MAE** = medically attended adverse event; **MedRA** = Medical dictionary for regulatory activities; **SPM** = study procedure manual

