Visit / Contact	Screening	V1	C1	V2 ¹	Monthly contacts until delivery ⁶	V3	V4	C2	Safety Visit - Event-driven	RSV-associated MA-RTI Visit - Event-driven ⁷	Notes
Timepoint	D (-28) – D 1	D1 (24 ^{0/7} - 36 ^{0/7} weeks of gestation)	D8	D31		Delivery	D43 Post-delivery	D181 Post-delivery			For monthly contacts: Section 8.4.2.1 Additional contacts and/or visits can be made between Visit-2 and the Delivery visit if deemed necessary.
Administer Intervention (study vaccine / placebo)		•									Sections 6.1 and 6.2
Record administered intervention number		•									
Observe for 30 minutes post-dose		0									
Distribute maternal participant card	0	0									Section 8.3.6
Record Labor / delivery information						•					
Record pregnancy / delivery outcomes (Day 1 post-study intervention to Day 42 post-delivery)		0	0		0	•	0				Section 8.3.3 . Must submit Expedited AE report for an adverse pregnancy outcome
Train maternal participant/LAR on use of eDiary device		0									Section 10.3.8
Distribute eDiary device to maternal participant / LAR.		0									
Review eDiary entries		0	0	0					0 ⁴	0 ⁴	Section 8.3.1
Return eDiary device				0							

CONFIDENTIAL

214725 (RSV MAT-012)
Protocol Amendment 1 Final

Visit / Contact	Screening	V1	C1	V2 ¹	Monthly contacts until delivery ⁶	V3	V4	C2	Safety Visit - Event-driven	RSV-associated MA-RTI Visit - Event-driven ⁷	Notes
Timepoint	D (-28) – D 1	D1 (24 ^{0/7} - 36 ^{0/7} weeks of gestation)	D8	D31		Delivery	D43 Post-delivery	D181 Post-delivery			For monthly contacts: Section 8.4.2.1 Additional contacts and/or visits can be made between Visit-2 and the Delivery visit if deemed necessary.
Concomitant medications / vaccinations		•	•	•	•	•	•	•	•	•	Sections 6.8.1 and 6.8.3
All solicited AEs (Day 1 post-study intervention to 7 days post-study intervention)		0	0						0		Sections 8.3.1, 10.3.4 and 10.3.8
All unsolicited AEs (Day 1 post-study intervention to 30 days post-study intervention)		•	•	•					•	•	Sections 8.3.1, 10.3.4 and 10.3.8
Record of worsening of pre-existing medical conditions and/or obstetric complications (Day 1 post-study intervention to 180 days post-delivery)		•	•	•	•	•	•	•	•	•	Section 8.2.1.2
Pregnancy-related AESIs (Day 1 post-study intervention to 42 days post-delivery)		•	•	•	•	•	•	•	•	•	Sections 8.3.1, 8.3.3, 8.3.4 and 10.3.5. Must submit an Expedited AE report.
Suspected, probable and confirmed cases of COVID-19 infection (depending on		•	•	•	•	•	•	•	•	•	Sections 8.4.7

CONFIDENTIAL

214725 (RSV MAT-012)

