Protocol Amendment 1 Final

Visit / Contact	Screening	V1	C1	V2 ¹	Monthly contacts until delivery ⁶	V3	V4	C2	Safety Visit - Event-driven	RSV-associated MA-RTI Visit - Event-driven ⁷	Notes
Timepoint	D (-28) – D 1	D1 (24 ^{0/7} - 36 ^{0/7} weeks of gestation)	D8	D31		Delivery	D43 Post-delivery	D181 Post-delivery			For monthly contacts: Section 8.4.2.1 Additional contacts and/or visits can be made between Visit-2 and the Delivery visit if deemed necessary.
the epidemiological COVID-19 situation) (Day 1 post-study intervention to 180 days post-delivery)											
MA-RTIs (Day 1 post-study intervention to 180 days post-delivery) ⁷		O ⁵	O ⁵	O ⁵	O ⁵	O ⁵	O ⁵	O ⁵		•	Sections 8.3.1, 8.3.3, 8.4 and 10.3.8 MA-RTIs for the maternal participants will no longer be performed.
SAEs, (S)AEs leading to study withdrawal, MAEs (Day 1 post-study intervention to 180 days post-delivery)		•	•	•	•	•	•	•	•	•	Sections 7.2, 8.3.1 and 10.3.8
SAEs related to study participation (Screening to Day 1 pre-study intervention)	•	•									Sections 8.3.1 and 10.3.8
Subsequent pregnancies							•	•	•	•	
Record interest in joining future extension study								•			Section 6.6

CONFIDENTIAL

214725 (RSV MAT-012)
Protocol Amendment 1 Final

Visit / Contact	Screening	V1	C1	V2 ¹	Monthly contacts until delivery ⁶	V3	V4	C2	Safety Visit - Event-driven	RSV-associated MA-RTI Visit - Event-driven ⁷	Notes
Timepoint	D (-28) – D 1	D1 (24 ^{0/7} - 36 ^{0/7} weeks of gestation)	D8	D31		Delivery	D43 Post-delivery	D181 Post-delivery			For monthly contacts: Section 8.4.2.1 Additional contacts and/or visits can be made between Visit-2 and the Delivery visit if deemed necessary.
Screening conclusion	●										
Study conclusion								●			Sections 4.4 and 10.1.9

V = visit; **C** = Contact; **D** = day; **MA-RTI** = medically attended respiratory tract illness; **LAR** = Legally acceptable representative

● is used to indicate a study procedure that requires documentation in the individual eCRF.

○ is used to indicate a study procedure that does not require documentation in the individual eCRF.

¹ Visit 2 (Day 31) may be replaced by Visit 3 (Delivery) in case of premature delivery. If the delivery date occurs prior to Day 31 post-study intervention, there will be no Visit 2 (Day 31).

² Fever is defined as temperature ≥38.0°C/100.4°F regardless of the location of measurement. The preferred location for measuring temperature in this study is the oral cavity.

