10.3.4. Unsolicited adverse events (AEs)

An unsolicited AE is an AE that was not included in a list of solicited events using a Participant Diary. Unsolicited events must have been spontaneously communicated by a maternal participant who has signed the informed consent/assent. Unsolicited AEs include both serious and non-serious AEs.

Potential unsolicited AEs may be medically attended (i.e., symptoms or illnesses requiring a hospitalization, or an emergency room visit, or visit to/by a health care provider). The maternal participants will be instructed to contact the site as soon as possible to report medically attended event(s), as well as any events that, though not medically attended, are of participant's concern. Detailed information about reported unsolicited AEs will be collected by qualified site personnel and documented in the participant's records.

Unsolicited AEs that are not medically attended or perceived as a concern by the maternal participant will be collected during an interview with the maternal participants and by review of available medical records at the next visit/contact.

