4.3.1.2.3. Analysis of unsolicited adverse events

The analysis of unsolicited events will be performed on Exposed Set.

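### The visit schedule and the protocol text disagree on asking about unsolicited AEs after an early delivery, so the primary 30-day percentage can be biased low

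*SAP*

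**What the plan says.** **Endpoint and denominator.** SAP 4.2.1.1 tabulates by group "The number and percentage of maternal participants reporting unsolicited AEs within 30 days" of dosing. SAP 4.3.1.2.3 sets the population: "The analysis of unsolicited events will be performed on Exposed Set". Completed 30-day follow-up is not a condition.

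**Schedule.** In Protocol Table 1 (Section 1.3) the row "All unsolicited AEs (Day 1 post-study intervention to 30 days post-study intervention") is marked at Visit 1, Contact 1, Visit 2 and the two event-driven visits. It is blank at the monthly contacts, Visit 3 (delivery), Visit 4 and Contact 2. Footnote 1 says "Visit 2 (Day 31) may be replaced by Visit 3 (Delivery) in case of premature delivery", and then "If the delivery date occurs prior to Day 31 post-study intervention, there will be no Visit 2 (Day 31").

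**Windows (Protocol Table 3).** Contact 1 is Day 8 to 12 and Visit 2 is Day 21 to 46. Visit 3 runs from 1 day before to 3 days after delivery, and Visit 4 is Day 31 to 61 after delivery.

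**Text.** Protocol 4.1 says unsolicited AEs are obtained by questioning at study visits and contacts, without naming which. Protocol 10.3.4, which the Table 1 row cites, tells women to report medically attended events and events of concern to the site promptly. The remaining events "will be collected during an interview with the maternal participants and by review of available medical records at the next visit/contact".

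**Missing coverage.** Protocol 9.4.1 leaves missing-data handling to the SAP. SAP 6.2.3 deals with partial dates, laboratory results, diary days and missing AE attributes. It has no rule for a woman whose 30-day window was not fully asked about.

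**The concern.** The table and the text give sites different instructions. Under the table, a woman who delivers before Day 31 may last be asked at Contact 1. Under 10.3.4, she would be asked again at Visit 3 and Visit 4. The blanks look deliberate, because neighbouring rows (AESIs, worsening of pre-existing conditions, SAEs and MAEs) are marked at those visits.

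If practice varied by site, the planned table could not show it: a woman not asked after Day 12 looks the same as a woman with no events. Coverage would also depend on the time from dosing to delivery. Protocol 2.3 reports that a preterm-birth imbalance in RSV MAT-009 led to the pause that preceded the stop in enrollment. Delivery timing may therefore differ between groups, and a between-group reading of this percentage needs to show how much of the window was covered in each.

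**Working it through.** **1. The plan's own figure.** SAP 5.1 gives the chance of seeing at least one AE among 252 vaccinees. 1 - (1 - p)^252 for p = 0.5%, 1% and 1.5% gives 71.7%, 92.1% and 97.8%, against the stated 72%, 92% and 98%. These reproduce, and they take all 252 women as fully observed. The plan gives no figure for partial coverage.

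**2. Who has no Visit 2.** Day 31 is 30 days after dosing, so delivery before Day 31 means at most 29 days after dosing. Term is 259 days or more, and 259 - 29 = 230 days = 32 6/7 weeks. A woman dosed at 32 6/7 weeks or later can therefore deliver at term without a Visit 2. One dosed at the upper limit of 36 0/7 weeks has none if she delivers by 36 0/7 weeks + 29 days = 40 1/7 weeks. The group is not confined to preterm births.

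**3. What each visit can cover.**
- Contact 1 alone covers 8 to 12 of the 30 days.
- Visit 3 falls at most 3 days after delivery. With delivery before Day 27, it leaves part of the window uncovered.
- Visit 4 always falls after Day 30, so a question there covers the whole window.
- A Visit 2 held on Days 21 to 30 also ends before or at the edge of the window, whatever the delivery date.

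**4. Which events are at risk.** Table 1 marks SAEs, MAEs and pregnancy-related AESIs at Visits 3 and 4, and SAP 6.2.3.4 counts SAEs in the unsolicited summaries. Protocol Table 17 limits the 30-day row to events outside these three classes. Loss can fall only on those events, and only when the woman does not report them herself.

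**5. Size.** The documents give no distribution of dosing or delivery and no AE risk. *Assumptions:* dosing uniform over 24 to 36 weeks; delivery normal with mean 37, 38 or 39 weeks and SD 2 weeks, more than 7 days after dosing and before 42 weeks; true 30-day risk 30% with constant hazard. A simulation gives the share delivering before Day 31 as about 23%, 18% and 13%.

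- *Nothing captured after Contact 1 (about Day 10).* Risk by Day 10 is 1 - 0.70^(10/30) = 11.2%, which is 0.112/0.30 = 37% of the true risk. Relative bias is -(share) × (1 - 0.37): -0.23 × 0.63 = -14%, -0.18 × 0.63 = -11%, -0.13 × 0.63 = -8%. A true 30% would read about 26% to 28%.
- *Visit 3 always substitutes, asked on the day of delivery:* -7%, -5%, -3%.
- *10.3.4 followed through Visit 4:* about zero.

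**6. Between groups.** Let f be the share delivering before Day 31 and m the share of their event-positive women who are missed. The observed percentage is p(1 - f·m). With p = 30% and f = 25% against 20%, the spurious difference is 30 × m × 0.05. That is 0.15 points at m = 10% and 1.5 points at m = 100%.

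**The case against.** The strongest reply is that a blank cell in a schedule does not mean no collection. Protocol 4.1 and 10.3.4 call for questioning at visits and contacts generally, and 10.3.4 adds that "The maternal participants will be instructed to contact the site as soon as possible to report medically attended event(s"). Visit 3 may stand in for Visit 2, and the more serious classes are collected at Visits 3 and 4 in any case. If sites worked to 10.3.4, nothing is lost. This stands. A reader might infer that Visits 3 and 4 carry no unsolicited-AE collection and that the percentage is therefore biased low. The documents support only that Table 1 schedules none there and that bias is possible.

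The larger percentages are also a limiting case. They treat every delivery before Day 31 as having no Visit 2. In the simulation about half of these deliveries (47% to 57%) fall on Days 22 to 30, when a Visit 2 could already have taken place. They also apply to the at-risk class of events, so the effect on the all-AE row is smaller.

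A reader might further infer that the vaccine will look safer than it is. That would require both a group difference in delivery timing in this trial and failure to ask after delivery, and the documents establish neither. Early delivery also generates AESIs and SAEs, which are captured.

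Finally, premature delivery in footnote 1 could mean below 37 weeks or simply before Day 31. The footnote does not settle whether Visit 3 may substitute after a term birth.

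What survives is the conflict between the table and the text, the full Exposed Set denominator, and the lack of any SAP provision that would show incomplete coverage.

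**Conclusion.** The point holds as a possible under-ascertainment of a primary safety percentage. If it occurs, it is downward and depends on delivery timing. It is confined to events that are not SAEs, MAEs or AESIs and are not self-reported. Its size is unknown from the documents. Under the dosing, delivery and risk assumptions above, the relative bias ranges from about zero to between -8% and -14%, with -3% to -7% if Visit 3 always substitutes. For a 5-point group difference in early delivery, the effect on the comparison is at most about 1.5 percentage points at a 30% risk. All analyses are descriptive, so no test is affected. The matter should be corrected, but it does not undermine the trial's main safety conclusions.

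**What to change.** **Protocol Table 1.** Reconcile the unsolicited-AE row with Sections 4.1 and 10.3.4. Mark it at Visits 3 and 4, for onset up to Day 30, for women without a completed Day-30 query. This reaches only women whose Visit 3 or 4 was still to come. Dosing stopped on 25 February 2022, so the last delivery before Day 31 could fall on 26 March 2022 and its Visit 4 window closed by about 26 May. That is before the SAP amendment of 1 June 2022. From then on the marks could help only women with a Visit 2 before Day 30 and a later delivery, so the SAP changes matter more.

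**SAP 4.2.1.1.** Keep the crude table on the Exposed Set, with SAEs and MAEs counted for all women. Add:
- by group, the number of women with no unsolicited-AE query at or after Day 30, and the days covered;
- a sensitivity table of the 30-day percentage restricted to women with complete coverage.

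Do not base a between-group reading on an estimate censored at the last query. It would discard SAEs and MAEs recorded later within the 30 days, and it would censor on delivery timing, which may depend on the vaccine.

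**Cost.** One or two extra tables from visit dates that should already be in the database, and one question at visits already scheduled where these are still to come. The restricted table is itself selected on delivery timing, so it is supportive only.
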